5.0 Analysis Populations and Important Subgroups

5.1 Analysis Populations

Intent-to-Treat Population Part 1

The Intent-To-Treat Part 1 (ITT Part 1) population comprises all subjects who were randomized and received at least one dose of the study medication during the Part 1 period. The data collected up to Week 16 will be included and analyzed by the treatment

group assignment given at the time of randomization, even if the subject does not receive the correct treatment, is not compliant to the protocol procedures, or does not follow the protocol until completion.

Intent-to-Treat Population Long Term

The Intent-To-Treat Long Term (ITT LT) population comprises all subjects who entered Part 2 period and received at least one dose of Part 2 study medication. The data collected from randomization and up to Week 32 will be included and analyzed by the four treatment regimens as follows:

- ADA 40 mg eow + MTX 15 mg ew/ADA 40 mg eow
- ADA 40 mg eow + MTX 15 mg ew/ADA 40 mg ew + MTX 15 mg ew
- MTX 20 - 25 mg or highest tolerable dose ew
- MTX 20 - 25 mg or highest tolerable dose ew/ADA 40 mg eow + MTX 20 - 25 mg or highest tolerable dose ew

Per Protocol Population

In order to evaluate the impact of major protocol violations on the results of the trial, additional analysis of the primary effectiveness variable may be conducted on the per protocol population, which consists of all ITT Part 1 subjects who entered the randomized period of the study and did not meet any major protocol violation during the Part 1 of the study. The determination of major protocol violation will be finalized prior to the final database lock.

Safety Population Part 1

The Safety population Part 1 consists of all subjects who received at least one dose of the study medication during the Part 1 period. The data collected up to Week 16 will be included and analyzed by the two "As treated" treatment groups in Part 1. "As treated" is determined by the treatment a subject received during majority of the subject's drug exposure time in the analysis period, regardless of the treatment randomized.

Safety Population Part 2

The Safety population Part 2 consists of all subjects who received at least one dose of the Part 2 study medication. The data collected from Week 16 to Week 32 will be included and analyzed by "as treated" treatment groups that subjects received when entering in Part 2. The data collected after the initiation of the rescue medication will be summarized separately, and not be included in the analysis.

"As treated" treatment groups are defined as follows:

1. ADA 40 mg eow
2. ADA 40 mg ew + MTX 15 mg ew
3. MTX 20 - 25 mg or highest tolerable dose ew
4. ADA 40 mg eow + MTX 20 - 25 mg or highest tolerable dose ew

Rescue Population

The Rescue population consists of all subjects who received at least one dose of the rescue medication after Week 24 visit. The data collected after the initiation of the rescue medication will be summarized separately by the Part 2 treatment groups as well as overall.

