8.1.2 Statistical and Analytical Plan

Complete and specific details of the final statistical analysis will be described and fully documented in the Statistical Analysis Plan (SAP). The SAP will be finalized prior to the database lock. The analysis will be performed using SAS (SAS Institute Inc., Cary, NC, USA).

Unless otherwise stated, all statistical tests will be conducted at $\alpha = 0.05$ level (2-sided). Descriptive statistics will be provided including but not limited to the number of observations, mean, standard deviation, median, minimum and maximum for continuous endpoints; and counts and percentages for binary endpoints.

A Week 16 database lock is planned when all randomized subjects have completed Week 16 (Part 1) of the study. The Week 16 study results (through Week 16) will be based on this database lock. Statistical comparisons for the primary and secondary efficacy endpoints will be performed at Week 16 between the Part 1 treatment groups. No multiplicity adjustment will be performed for the statistical tests since there is only one primary endpoint.

Data from the subsequent period (Part 2) will be reported at the completion of the study by Part 2 treatment groups.

The last available pre-treatment values recorded on or before Day 1 (the first dose of Part 1) will be considered as the Baseline value for efficacy analysis. All subsequent study visits will be determined in reference to the baseline.

To account for missing data for the binary efficacy endpoints, a non-responder imputation approach (NRI) will be used, i.e., subjects who discontinue during Part 1 with missing data will be imputed as a non-responder. For continuous endpoints, the Mixed-effects Model Repeated Measures (MMRM) analysis based on all observed data will be used.

The rescued patients' last observation on or before the rescued visit will be included in the analysis of Part 2 treatments. The efficacy and safety after the rescue will be summarized separately for the rescued patients.

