- Arm 3/Part 2: Subjects achieving MDA at Week 16 on MTX escalated to 20 - 25 mg or highest tolerable dose ew, will continue with the same MTX dose (MTX 20 - 25 mg or highest tolerable dose ew),
- Arm 4/Part 2: Subjects not achieving MDA at Week 16 on MTX escalated to 20 - 25 mg or highest tolerable dose ew, will receive ADA 40 mg eow in

combination with MTX 20 - 25 mg or highest tolerable dose ew (ADA 40 mg eow plus MTX 20 - 25 mg or highest tolerable dose ew).

Subjects in Arms 1 - 4 of Part 2 of the study will have the option of being rescued, starting at Week 24 and based on the subject not achieving MDA and the Investigator's judgment. The selection of the rescue treatment regimen will be at the discretion of the Investigator, but should involve ADA and/or MTX and should not involve prohibited medications per the protocol.

A schematic of the study design is shown below in [Figure 1](#):

Figure 1. A schematic of the study design

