7.2.1.1 Adverse Event Overview

The number and percentage of subjects experiencing TEAEs will be summarized for the following AE categories by the two treatment groups in Part 1 and by the four treatment groups in Part 2:

- All TEAEs
- Treatment-emergent serious adverse events (SAEs)
- Treatment-emergent severe adverse events
- TEAEs reasonably possibly related to study drug
- TEAEs leading to discontinuation of study drug
- TEAE leading to death

Additional AEs may be considered for tabulation/summary based on recommendations from Clinical and Safety as deemed appropriate.

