7.2.1.2 Adverse Events by System Organ Class and Preferred Term

The number and percentage of subjects experiencing adverse events will be tabulated by SOC and MedDRA PT by the two treatment groups in Part 1 and by the four treatment groups in Part 2. The SOCs will be presented in alphabetical order, and the PTs will be presented in alphabetical order within each SOC.

Subjects reporting more than one adverse event for a given MedDRA preferred term will be counted only once for that term (most severe incident for the severity tables and most related incident for the relationship tables). Subjects reporting more than one type of adverse event within a SOC will be counted only once for that SOC. Subjects reporting more than one type of adverse event will be counted only once in the overall total.

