7.2.2 SAEs (Including Deaths) and Adverse Events Leading to Study Drug Discontinuation

All serious adverse events (SAEs), deaths, and adverse events leading to discontinuation of study drug will be listed. The number and percentage of subjects experiencing SAEs (including deaths) and adverse events leading to discontinuation of study drug will be tabulated according to the primary MedDRA SOC and MedDRA PT for each treatment group in Part 1 and for each treatment groups in Part 2.

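### Part 2 adverse-event tables stop counting at rescue but give only crude percentages, so arms with more or earlier rescue could show lower figures merely because they are observed for less time

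*SAP*

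**What the plan says.** **Denominator (SAP 5.1).** "The Safety population Part 2 consists of all subjects who received at least one dose of the Part 2 study medication". A rescued subject therefore stays in it.

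**Numerator (SAP 5.1).** The window runs over Part 2: "The data collected from Week 16 to Week 32 will be included and analyzed by" the regimen on entering Part 2. It is then cut at rescue: "The data collected after the initiation of the rescue medication will be summarized separately, and not be included in the analysis". Protocol 8.1.2 agrees: "The efficacy and safety after the rescue will be summarized separately for the rescued patients". SAP 5.1 also defines a Rescue Population, whose post-rescue data are shown by Part 2 group and overall.

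**Rescue timing (SAP 4.2.1).** Subjects in all four arms "will have the option of being rescued, starting at Week 24", if not in MDA and if the investigator so judges. SAP 6.6 expects rescue at Weeks 24 and 28.

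**Statistic.**
- Overview (SAP 7.2.1.1): "The number and percentage of subjects experiencing TEAEs will be summarized for the following AE categories".
- By term (SAP 7.2.1.2): "The number and percentage of subjects experiencing adverse events will be tabulated by SOC and MedDRA PT".
- Serious and discontinuation events (SAP 7.2.2): "The number and percentage of subjects experiencing SAEs (including deaths) and adverse events leading to discontinuation of study drug will be tabulated".
- The severity, relationship and special-interest tables (SAP 7.2.1.3, 7.2.1.4, 7.2.1.6) mention no person-time either.

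The only reference to an incidence rate is a footnote in SAP Appendix A about the CD programme. Protocol 8.1.3 promises a summary of treatment duration but does not tie it to adverse events.

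**Event window (SAP 7.2.1).** A Part 2 event counts as treatment-emergent up to 70 days after the last adalimumab dose or 30 days after the last MTX dose. This definition has neither a rescue cut-off nor a Week 32 limit, so it does not match SAP 5.1.

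**The concern.** A subject rescued at Week 24 counts fully in the denominator but supplies about 8 of the 16 Part 2 weeks. If rescue is unequal across arms, the crude percentages rest on unequal follow-up, and nothing in the tables shows this.

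Rescue requires not being in MDA. Arms 2 and 4 consist of subjects who missed MDA at Week 16, and Arms 1 and 3 of those who reached it, so unequal rescue is plausible. Arm 2 receives weekly adalimumab, which Protocol 3.4 and 5.6.4 describe as the exception to the approved dosing in PsA, so its safety column will be read with interest. At stake is the descriptive reading of four adjacent columns. No test is affected.

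**Working it through.** The documents state no figure for Part 2 safety, so there is none to reproduce. The check is how far truncation at rescue moves a crude percentage when the true risk is the same in every arm.

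**Inputs from the documents.** Part 2 lasts 16 weeks (SAP 5.1). Rescue is possible from Week 24 (SAP 4.2.1), with Week 28 as the second point (SAP 6.6). A rescued subject thus contributes T = 8 or T = 12 weeks.

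**Assumptions, not in the documents.** True 16-week risk R of 20%, 40% or 60%; constant hazard, equal across arms; share rescued r from 0% to 50%; all rescue in an arm at one visit.

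**Formula.** Risk in T weeks = 1 − (1 − R)^(T/16). Crude percentage = (1 − r) × R + r × [1 − (1 − R)^(T/16)].

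**Worked case, R = 40%.**
- T = 8: 1 − 0.60^0.5 = 22.5%. With r = 25%: 0.75 × 40 + 0.25 × 22.5 = 35.6%. With r = 50%: 0.5 × 40 + 0.5 × 22.5 = 31.3%.
- T = 12: 1 − 0.60^0.75 = 31.8%. With r = 25%: 0.75 × 40 + 0.25 × 31.8 = 38.0%. With r = 50%: 0.5 × 40 + 0.5 × 31.8 = 35.9%.

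**Range.** Crude percentage shown with 10% / 30% / 50% rescued:

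| True 16-week risk | Rescue at Week 24 | Rescue at Week 28 |
|---|---|---|
| 20% | 19.1 / 17.2 / 15.3 | 19.5 / 18.6 / 17.7 |
| 40% | 38.3 / 34.8 / 31.3 | 39.2 / 37.5 / 35.9 |
| 60% | 57.7 / 53.0 / 48.4 | 59.0 / 56.9 / 54.9 |

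For Week 24 rescue the shortfall runs from 0.9 points (20 − 19.1) to 11.6 points (60 − 48.4). Comparing an arm with 10% rescued at Week 24 with one with 40% rescued, a hazard about 1.20 to 1.23 times higher in the second arm would give the same crude percentage.

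**Uncommon events.** The planning rates in SAP 4.4 (40% and 20% MDA, 120 per arm) imply Part 2 arms of about 48, 72, 24 and 96 before dropout. Take an assumed 5% risk, for which the 8-week risk is 1 − 0.95^0.5 = 2.53%.
- Arm 2 (72 subjects): 3.6 affected subjects expected with no rescue. With 25% rescued at Week 24, 72 × (0.75 × 5% + 0.25 × 2.53%) = 3.2. With 50% rescued, 2.7. The change is under one subject.
- Arm 4 (96 subjects, the largest): 4.8 falls to 4.2 with 25% rescued and to 3.6 with 50%. The change passes one subject only at that extreme.

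**Rate with time ending at rescue.** Under the same model, first events divided by time to first event or rescue give 72.8, 166.6 and 298.8 per 100 patient-years for R = 20%, 40% and 60%, whatever share is rescued.

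**Effect of the unreconciled window.** If the 70-day tail applied only to unrescued subjects, they would be followed 16 + 10 = 26 weeks against 8. At R = 40% the 26-week risk is 1 − 0.60^(26/16) = 56.4%. The crude figure is then 0.9 × 56.4 + 0.1 × 22.5 = 53.0% with 10% rescued, and 39.5% with 50% rescued. The definition of time at risk therefore matters as much as the choice of statistic.

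**The case against.** Splitting at rescue is a normal on-regimen approach, since the subject is on a different regimen afterwards. A reader might infer that post-rescue events disappear. They do not: the Rescue Population summary shows them by originating Part 2 group. That stands, although a separate table does not put the four main columns on a common time base.

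Part 2 arms are set by Week 16 MDA status and not randomised, and the only between-group safety test planned is the Part 1 laboratory ANOVA (SAP 7.3.1). Anyone comparing columns already faces confounding by response and prior regimen, which a rate does not cure. That also stands, and limits the point to descriptive reading.

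A reader might infer that rescue will differ strongly between Arms 1 and 3 and Arms 2 and 4, so that weekly adalimumab will look safer than it is. The documents do not support that. They give no rescue proportions, and rescue depends on MDA from Week 24 onward plus judgment, not on Week 16 status. Arm 1 stops MTX at Week 16 and could lose MDA; Arm 4 receives adalimumab for the first time.

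Finally, rates can mislead too. If the hazard in the first 8 Part 2 weeks were twice that in the next 8 (an assumption), in relative units an unrescued arm would show (16 + 8)/16 = 1.50. An arm with 50% rescued at Week 24 would show (0.5 × 24 + 0.5 × 16)/12 = 1.67, which is 11% higher with identical underlying risk. This argues for showing both statistics, not for leaving the percentages alone.

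**Conclusion.** The point holds as a cheap improvement, not as an error. A full denominator, data truncated at rescue and crude percentages together lower the reported figure in an arm with more or earlier rescue, all else equal. Under a constant hazard, a true 40% would read 35.6% or 31.3% with 25% or 50% rescued at Week 24, and 38.0% or 35.9% at Week 28. For uncommon events the change is a fraction of a subject in most scenarios. Those sizes rest on assumed risks, rescue shares and rescue times. The documents establish the mechanism but not how large the imbalance will be or which arm it will favour.

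**What to change.** Keep the crude percentages. In the Part 2 TEAE, SAE and AESI tables add, for each of the four groups, the number of events, total patient-years at risk, and events per 100 patient-years, with time at risk ending at the start of rescue.

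State one time-at-risk definition and use it for both numerator and denominator. It must reconcile the Week 16 to 32 window and rescue cut-off in SAP 5.1 with the 70/30-day window in SAP 7.2.1, and say whether the post-dose tail applies after rescue. Add a footnote that Part 2 groups are not randomised and that the rates assume a roughly constant hazard.

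The cost is small. Dosing dates and event onset dates are already collected (Protocol 5.5.6 and 6.1), and SAP 3.0 allows exploratory analyses to be added. The downsides are longer tables and a statistic that is comparable across arms only when hazards are roughly constant; it does not remove confounding by Week 16 response or prior regimen.

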5.2 Subgroup

Age, gender, BMI, race, region, prior MTX use (> 3 months or ≤ 3 months) will be the subgroups for the subgroup analysis.

6.0 Efficacy Analyses

6.1 General Considerations

There are two sets of planned efficacy analysis: Part 1 analysis and long-term analysis.

Part 1 Efficacy Analysis

Standard efficacy analysis by the randomized treatment groups (ADA 40 mg eow + MTX 15 mg ew, MTX 20 - 25 mg or highest tolerable dose ew) will be performed on the efficacy data up to Week 16 based on ITT Part 1 population. Formal statistical inference will be generated with missing data handling, and statistical testing will be conducted at $\alpha = 0.05$ level (2-sided). Results from this set of analysis will be used as the key efficacy findings of this study.

No protocol-defined rescue will occur prior to the time point.

Long Term Efficacy Analysis

Long term efficacy analysis from baseline to Week 32 will be performed based on the ITT LT Population by the 4 treatment regimens as described in Section 5.1. Descriptive statistics will be summarized by the four treatment regimens. The between-treatment comparison is not applicable for the long term analysis. No missing data imputation will be performed for long term efficacy analysis.

Rescue handling will be applied for long term efficacy analysis. The data collected after the initiation of the rescue medication will be summarized separately.

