4.7 Missing Data Imputation

The following missing data imputation will be performed for efficacy analysis.

Non-Responder Imputation (NRI) Approach

To account for missing data for the binary efficacy endpoints, a non-responder imputation approach (NRI) will be used, e.g., subjects who have missing data at a specific visit will be treated as non-responder for that visit, or who prematurely discontinue or have been rescued will be considered as a non-responder for all subsequent visits.

Mixed-Effects Model Repeated Measures (MMRM)

The repeated measure analysis will be conducted using mixed models based on observed data at all visits. For the MMRM analysis (of continuous variables), data collected after premature discontinuation of study drug will be excluded. The mixed model includes treatment, visit, treatment-by-visit interaction, and the stratification factor of duration of prior MTX use (≤ 3 months or > 3 months) as fixed effects, subject as random effect and baseline measurement as a covariate. An unstructured variance covariance matrix will be used. The parameter estimations assume data being missing at random (MAR) and using the method of restrictive maximum likelihood (REML).

Observed Cases (OC)

The OC analysis will not impute values for missing evaluations, and thus a subject who does not have an evaluation on a scheduled visit will be excluded from the OC analysis for that visit. In addition, OC will not include values after subject have rescue visit or after premature discontinuation of study drug.

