6.2 Primary Efficacy Analysis

The primary endpoint is the proportion of subjects achieving MDA at Week 16. The null hypothesis is that there is no difference in the rate of MDA between the two randomized treatment groups of ADA 40 mg eow + MTX 15 mg ew and MTX 20 - 25 mg or highest tolerable dose ew; the alternative hypothesis is that the rates of MDA between the two groups are different.

Point estimate and 95% CI using normal approximation will be provided for the rate of MDA for each randomized treatment group. Treatment comparisons will be made between the randomized treatment groups using a Cochran-Mantel-Haenszel (CMH)

test^{5,6} (refer to Appendix A), adjusting for the stratification factor which is the duration of prior MTX 15 mg ew use of ≤ 3 months or > 3 months. Point estimate of the treatment difference and the associated 95% CI using normal approximation will also be presented. To account for missing data for the primary endpoint, a non-responder imputation approach (NRI) will be used, e.g., subjects who discontinue during Part 1 with missing data will be imputed as a non-responder (NRI) in the subsequent visits.

Sensitivity analyses will be conducted using the same method described above based on observed cases (OC) data.

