6.3 Secondary Efficacy Analyses

Part 1 Analysis

A complete list of secondary efficacy endpoints is provided in Section 4.3.2. Binary endpoints will be analyzed in a similar way as the primary endpoint.

For the continuous endpoints, the change from baseline at Week 16 will be analyzed using MMRM with treatment, the stratification factor of duration of prior MTX use (≤ 3 months or > 3 months), visit, and treatment-by-visit interaction as fixed effects, subject as random effect and baseline measurement as a covariate. The MMRM analysis is based on observed data. The LS mean, 95% CI and standard error for each randomized treatment group, the LS mean of the treatment difference and its associated 95% CI and p-value from the MMRM model will be presented.

Long Term Analysis

The achievement of MDA at Week 32 on each of the four different treatment regimens will be evaluated. The proportion of subjects who achieved MDA at Week 32 will be summarized by counts and percentages for the four treatment regimens. Point estimate and 95% CI using normal approximation will be provided for each treatment regimen as well. The subjects who were rescued prior to Week 32 will be considered as non-

responders (MDA = 0) at Week 32. No comparison between treatment regimens will be performed.

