6.4 Other Efficacy Analyses

Clinical Efficacy Variables

Binary secondary endpoints described in Section 4.3.2 will be analyzed as exploratory endpoints at Week 32 using count and percentages on each of the four different treatment regimens. Point estimate and 95% CI using normal approximation will be provided as well. The data occurred after initiation of the rescue medication will be imputed using NRI for the subsequent visits in this summary.

Continuous secondary endpoints described in Section 4.3.2 will be analyzed as exploratory endpoints at Week 32 by summary statistics (number of subjects, mean, 95% confidence interval, standard deviation, median, minimum, maximum) for each treatment regimen. All observed data will be used to summarize the continuous exploratory endpoints. The data occurring after initiation of the rescue medication will be overwritten by the last observation prior to treatment rescue (Last observation carried forward: LOCF) for the subsequent visits in this summary.

Ultrasound Variables

For ultrasound assessment at Week 16, analysis will be performed using similar methods to those described for the secondary continuous efficacy endpoints. In addition, baseline weight will also be included as an additional covariate in MMRM. The LS mean, 95% CI and standard error for each randomized treatment group and the LS mean of the treatment difference, its associated 95% CI and p-values will be presented.

For the ultrasound assessment at Week 32, summary statistics (number of subjects, mean, 95% confidence interval, standard deviation, median, minimum, maximum) will be presented for each treatment regimen. All observed data will be used to summarize the

continuous exploratory endpoints. The data occurring after initiation of the rescue medication will be overwritten by LOCF for the subsequent visits in this summary.

Summary of Efficacy Endpoints by Visit

Summary of the primary and secondary efficacy endpoints at the scheduled time points will be presented by two treatment groups in the Part 1 analysis and by four treatment regimens in the long-term analysis. Achievement of each MDA component as binary endpoints will be summarized similarly as well.

For Part 1 analysis, binary efficacy endpoints will be analyzed in a similar way as the primary endpoint and continuous efficacy endpoints will be analyzed from the same MMRM model for the Wk16 endpoints.

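### For Week 32 MDA, SAP 4.7 and SAP 6.1 conflict on unrescued subjects with no Week 32 assessment, and the denominator to use for them is not stated

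*SAP*

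**What the plan says.** SAP 4.7 introduces its rules as applying to efficacy analysis in general and sets non-responder imputation (NRI) for the binary endpoints. It says that "subjects who have missing data at a specific visit will be treated as non-responder for that visit", and that subjects "who prematurely discontinue or have been rescued will be considered as a non-responder for all subsequent visits".

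SAP 6.1, under the long-term analysis, names the ITT Long Term (ITT LT) population by regimen. It then says "No missing data imputation will be performed for long term efficacy analysis", and separately "Rescue handling will be applied for long term efficacy analysis".

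SAP 6.3 covers the endpoint itself: "The proportion of subjects who achieved MDA at Week 32 will be summarized by counts and percentages for the four treatment regimens", with a normal-approximation 95% CI. Its only rule for incomplete subjects concerns rescue: "The subjects who were rescued prior to Week 32 will be considered as" non-responders. SAP 6.4 does the same for the other binary endpoints at Week 32: "The data occurred after initiation of the rescue medication will be imputed using NRI for the subsequent visits in this summary". The by-visit summary in 6.4 also covers rescued subjects only. For the continuous Week 32 endpoints, 6.4 states that observed data are used; it has no matching sentence for the binary ones.

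**The concern.** A subject who enters Part 2, is never rescued and has no Week 32 MDA is a failure under 4.7 and is not imputed under 6.1. Nothing says which section prevails, so two programmers working from the same SAP could report different Week 32 rates and intervals.

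The choice matters because of when rescue opens. Both documents allow it only from Week 24, so everyone who leaves Part 2 before then is unrescued by design, whatever the reason for leaving. If such subjects are dropped from the percentage while rescued subjects are kept as failures, two kinds of unsuccessful course are treated differently, and the summary favours the regimen. In an open-label trial it is also better not to leave this choice until the data can be seen.

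**Working it through.** The plan gives no figure for Week 32 MDA, so there is none to reproduce. The check is first textual, then arithmetic.

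**Where the rules differ**

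| Subject in ITT LT | SAP 4.7 | SAP 6.1 with 6.3 and 6.4 |
|---|---|---|
| On study, unrescued, Week 32 MDA available | as observed | as observed |
| Rescued before Week 32 | non-responder | non-responder |
| Unrescued, no Week 32 MDA | non-responder | not imputed; place in the denominator not stated |

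Only the last row is in conflict.

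**Does 4.7 reach Part 2?** Yes. Its NRI sentence covers rescued subjects, and SAP 6.1 itself notes that no protocol-defined rescue occurs before the Part 1 time point. The rescue clause can therefore operate only in Part 2.

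**Does another passage settle it?** No. Protocol 8.1.2 ties NRI to discontinuation during Part 1 and otherwise addresses rescued subjects. SAP 4.7 defines an observed-cases analysis that would exclude these subjects, but 6.1 and 6.3 do not call for it at Week 32.

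**Formula.** Let N be the ITT LT count in a regimen, X the responders (rescued subjects already counted as failures), M the unrescued subjects with no Week 32 MDA, and m = M/N.

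- NRI as in 4.7: X/N.
- 6.1 with missing subjects kept in the denominator and shown as missing: X/N, the same rate.
- 6.1 with assessed subjects only: X/(N − M) = (X/N) × 1/(1 − m).

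**Size by assumed rate.** Part 2 missingness and Week 32 rates are assumptions. The 10% is borrowed from the Week 16 sample-size allowance (SAP 4.4), the only dropout figure in the documents.

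| Assumed NRI rate | m = 5% | m = 10% |
|---|---|---|
| 30% | 30/0.95 = 31.6% (gap 1.6) | 30/0.90 = 33.3% (gap 3.3) |
| 50% | 50/0.95 = 52.6% (gap 2.6) | 50/0.90 = 55.6% (gap 5.6) |
| 70% | 70/0.95 = 73.7% (gap 3.7) | 70/0.90 = 77.8% (gap 7.8) |

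**Size by arm.** Protocol 8.2 assumes Week 16 rates of 40% and 20% with 120 per arm. With no dropout, the Part 2 arms are 120 × 0.4 = 48, 120 × 0.6 = 72, 120 × 0.2 = 24 and 120 × 0.8 = 96. Take an assumed 50% NRI rate and about 10% unrescued missing (5, 7, 2 and 10 subjects), with the interval p ± 1.96√(p(1−p)/n):

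| Part 2 arm | NRI, X/N (95% CI) | Assessed only, X/(N−M) (95% CI) | Gap |
|---|---|---|---|
| 1 | 24/48 = 50.0% (35.9–64.1) | 24/43 = 55.8% (41.0–70.7) | 5.8 |
| 2 | 36/72 = 50.0% (38.5–61.5) | 36/65 = 55.4% (43.3–67.5) | 5.4 |
| 3 | 12/24 = 50.0% (30.0–70.0) | 12/22 = 54.5% (33.7–75.4) | 4.5 |
| 4 | 48/96 = 50.0% (40.0–60.0) | 48/86 = 55.8% (45.3–66.3) | 5.8 |

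The intervals overlap heavily.

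**The case against.** The best reply is that the SAP comes close to answering the question. SAP 6.1 describes the Part 1 analysis as done with missing-data handling, then rules out imputation for the long-term analysis. Placed together, these sentences look like a deliberate split, and the specific text would normally prevail over the general one. SAP 6.2 illustrates NRI with Part 1: "subjects who discontinue during Part 1 with missing data will be imputed as a non-responder (NRI) in the subsequent visits". The rescue-only rules in 6.3 and 6.4 would be redundant if all of 4.7 applied, and they fit the separate rescue handling that 6.1 announces.

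Most of this stands. A reader might infer that the SAP holds two equally weighted rules with nothing to choose between them. The text does not support that, because the contrast in 6.1 favours 6.1. But the precedence has to be inferred, and 4.7 does extend into Part 2.

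A second reply is that ruling out imputation does not by itself remove anyone from a denominator: ITT LT is the named population, and X/N with missing shown as missing also involves no imputation. That is correct, and it shows that even someone who follows 6.1 faithfully has two possible rates.

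The third is that the sizes are illustrative. That also stands. Subjects who drop out in Part 1 never enter ITT LT, so the borrowed 10% is only a scale. A uniform 50% is applied to arms selected as Week 16 responders (1 and 3) or non-responders (2 and 4). How many would leave before Week 24 is unknown.

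**Conclusion.** The conflict is real but narrow. It concerns unrescued ITT LT subjects with no Week 32 MDA. SAP 6.1 is probably meant to govern, but the SAP does not say so and does not say what the denominator then is. Applied to assessed subjects only, 6.1 gives the NRI rate times 1/(1−m): about 5.6 points higher at an assumed 50% rate and 10% unrescued missing, and 1.6 to 7.8 points over the assumed ranges shown.

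Three stronger conclusions that a reader might draw are not supported:

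- That following 6.1 always raises the rate. It does so only if missing subjects leave the denominator and the regimen has at least one responder and one such subject.
- That the analysis set is undefined. ITT LT is named; what is missing is whether it is the percentage denominator when Week 32 MDA is absent.
- That the trial's main result is at risk. Week 32 MDA is untested and not compared between regimens, SAP 6.1 designates the Part 1 results as the key efficacy findings, and the primary analysis, alpha and power are unaffected.

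Severity is minor to moderate. It is worth correcting because this is the only Part 2 secondary endpoint and it is reported with an interval for each regimen.

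**What to change.** Reconcile 4.7 and 6.1 in the text:

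- In SAP 6.1, limit the no-imputation sentence to continuous long-term endpoints, for which 6.4 already specifies observed data.
- In SAP 6.3, SAP 6.4 and the by-visit summary, state that binary long-term endpoints use the ITT LT count of the regimen as denominator, with missing, discontinued or rescued subjects as non-responders, as in 4.7.

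Simply declaring that 6.1 prevails with an assessed-subject denominator would also end the ambiguity. It would keep the asymmetry in which rescued subjects fail and unrescued leavers disappear, which is why the NRI wording is preferable. The carry-forward rule after rescue for continuous endpoints stays as it is, and no extra observed-cases analysis is needed.

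The cost is a few SAP sentences, with no new data or analyses. Reported Week 32 rates will be slightly less favourable than with an assessed-subject denominator.
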